## 4.5. Tertiary Endpoint Analysis

### 4.5.1. Tertiary Efficacy Endpoints

Analysis for fasting serum glucose will be based on both EAS1 and EAS2 similar to those described in Section 4.4.2.1. Patient reported outcomes will be based on EAS2.

Treatment comparison for the proportion of participants achieving HbA1c target (<7% or ≤6.5%) will be analyzed using the same method for the key secondary endpoint.

#### 4.5.2. Tertiary Safety Endpoints

For tertiary safety measures, the details are provided in Section [4.6](#) and the following subsections.

#### 4.5.3. Participant Reported Outcome

The analyses for participant-reported outcomes will be based on the EAS2 data.

##### 4.5.3.1. Basal Insulin Experience

###### Likelihood of incorporating into routine

This is a Lilly-developed, participant-completed question to understand the participant's likelihood of incorporating their study insulin into their diabetes management routine. The question is rated on a 5-point scale with responses ranging from "very unlikely" to "very likely."

The frequency and proportion of the last non-missing responses up to Week 26 (Visit 23) will be summarized by study treatment and using Wilcoxon rank sum test for treatment comparison.

###### Preference

This is a Lilly-developed, participant-completed question to understand the participant's preference for their pre-study or current study treatment. The question is rated on a 5-point scale with responses ranging from "strongly prefer the study insulin" to "strongly prefer my previous insulin." The question also includes a "not applicable" option for participants that stayed on the same insulin in the treatment phase.

The frequency and proportion of the last non-missing responses up to Week 26 (Visit 23) will be summarized by study treatment and using Wilcoxon rank sum test for treatment comparison.

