#### Type of participant and disease characteristics

2. Have a diagnosis of T2D according to the WHO criteria, currently treated with basal insulin and at least 2 injections of prandial insulin per day.
3. Are receiving  $\geq 10$  units of total basal insulin per day at screening (Visit 1).
4. Are receiving  $\leq 2$  units/kg/day of total daily insulin at screening (Visit 1).
5. Have an HbA1c value of 7.0% to 10%, inclusive, as determined by the central laboratory at screening (Visit 1).
6. Have been treated with a stable regimen of one of the following basal insulins used according to local product label with or without noninsulin diabetes therapy for at least 90 days prior to screening (Visit 1).
  - once daily U-100 or U-200 insulin degludec
  - once daily U-100 or U-300 insulin glargine
  - once or twice daily U-100 insulin detemir (Levemir® [Novo Nordisk A/S., Bagsvaerd, Denmark]), or
  - once or twice daily human insulin Neutral Protamine Hagedorn.
7. Have been treated with at least twice daily dosing of any of the following insulins used according to local product label for at least 90 days prior to screening (Visit 1). One dose of prandial insulin must occur at the evening meal.
  - Insulin lispro (U-100 and U-200)
  - Insulin lispro-aabc (Lyumjev™ [Eli Lilly and Co., Indianapolis, IN], U-100 or U-200)
  - Insulin aspart (U-100; including Fiasp® and NovoLog® [Novo Nordisk A/S., Bagsvaerd, Denmark])
  - Insulin glulisine (U-100), or
  - Regular insulin (U-100).
8. Acceptable noninsulin diabetes therapies may include 0 to up to 3 of the following with a stable dose for at least 90 days prior to screening (Visit 1).
  - dipeptidyl peptidase IV inhibitors

- sodium-glucose co-transporter-2 inhibitors
- biguanides (for example, metformin), or
- glucagon-like peptide-1 receptor agonists.

Note: All noninsulin diabetes therapies must be used in accordance with the corresponding local product label at the time of screening (Visit 1), and participants should be willing to continue stable dosing throughout the study according to the protocol.

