### **8.1.2.3. Basal Insulin Experience: Preference**

The Basal Insulin Experience: Preference is a self-report scale consisting of a single question to understand the participant's preference for their pre-study or current study treatment. The question is rated on a 5-point scale with responses ranging from "strongly prefer the study insulin" to "strongly prefer my previous insulin." The question also includes a "not applicable" option for participants that stayed on the same insulin in the treatment phase.

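### The SAP gives no rule for 'not applicable' in the preference rank test, and dropping those answers would remove prior-glargine users from one arm only

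*SAP*

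**What the plan says.** SAP 4.5.3.1 (Preference) describes a single question on whether the participant prefers the study insulin or the one used before. "The question is rated on a 5-point scale with responses ranging from" a strong preference for the study insulin to a strong preference for the previous one. Outside that scale there is a not-applicable "option for participants that stayed on the same insulin in the treatment phase". Protocol 8.1.2.3 describes the item in the same way.

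For the analysis, the SAP takes each participant's latest available answer through Week 26. These answers are "summarized by study treatment and using Wilcoxon rank sum test for treatment comparison". SAP 4.5.3 adds the data set: "The analyses for participant-reported outcomes will be based on the EAS2 data". Neither document says whether a not-applicable answer is dropped, ranked, or dealt with by restricting the comparison.

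Two other parts of the protocol decide who can use the option. Inclusion criterion 6 (Protocol 5.1) lists the permitted pre-study basal insulins, including "once daily U-100 or U-300 insulin glargine", along with degludec, detemir and NPH. LY3209590 is not on the list, and exclusion criterion 37 (Protocol 5.2) bars people already dosed with it in another study. Protocol 6.1 gives the study glargine as 100 units/mL.

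**The concern.** Everyone assigned to LY3209590 changes basal insulin. In the glargine arm, a participant who came in on U-100 glargine does not. The option therefore applies in one arm only, and a rank test has no natural place for it.

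The item asks for a comparison with the previous insulin, so the answer may well depend on what that insulin was. If one arm loses its prior-glargine users and the other keeps them, a difference between arms can come from the mix of previous insulins alone. Pre-study insulin is balanced by randomization only in the full arms, and the planned test has no covariate that could restore the balance. At stake is a preference p-value that a reader would take as a randomized comparison.

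**Working it through.** The plan states no power or sample size for this item, so there is no figure of its own to reproduce.

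**Inputs from the documents**
- Completers per arm: 670 / 2 = 335 randomized, and 335 × 0.85 = 284.75, in line with the stated 284 (SAP 5).
- Test: two-sided Wilcoxon rank sum, taken at the 0.05 level of Protocol 9.3.1.

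**Assumptions, because the documents give neither**
- Share *g* of participants to whom the option would apply if assigned to glargine: 20%, 40% or 60%.
- Shift *d* between the answers of these prior-glargine users and those of other participants, in SD units on a latent normal scale: 0, 0.25, 0.5 or 0.75. Among the other participants each of the five responses has probability 20%.
- No treatment effect: the answer depends on the previous insulin and not on the assigned arm.

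**Reading 1: not-applicable answers are dropped.** The glargine arm keeps 284 × (1 − *g*) answers: 227, 170 or 114. The LY3209590 arm keeps all 284. The latent means of the compared groups then differ by *g* × *d* with no treatment effect; for example, 0.4 × 0.5 = 0.20 SD. Simulated rejection rates, 3,000 trials per cell:

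| Share *g* | Answers used (LY3209590 / glargine) | *d* = 0 | *d* = 0.25 | *d* = 0.5 | *d* = 0.75 |
|---|---|---|---|---|---|
| 20% | 284 / 227 | 5.3% | 7.9% | 16.8% | 31.4% |
| 40% | 284 / 170 | 4.9% | 15.8% | 48.3% | 78.6% |
| 60% | 284 / 114 | 4.3% | 23.2% | 69.9% | 94.2% |

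**Reading 2: not-applicable is given a rank.** Suppose it is placed at one end of the scale, *g* = 20%, and the remaining answers have the same distribution in both arms. The probability that an LY3209590 answer outranks a glargine answer, counting ties as half, becomes 0.2 × 1 + 0.8 × 0.5 = 0.60 instead of 0.50. Ignoring ties, the null standard error is √[(284 + 284 + 1) / (12 × 284 × 284)] = √(569 / 967,872) = 0.0242. The expected z is 0.10 / 0.0242 = 4.1, so the test would nearly always reject. Placing the category at the other end gives 0.40 and z = −4.1. The coding choice alone settles the direction of the result.

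**Reading 3: both arms are restricted to participants not on that glargine before the study.** In the same simulated trials the rejection rate is 4.2% to 5.8% over all twelve cells. The Monte Carlo margin around 5% is 1.96 × √(0.05 × 0.95 / 3,000) = 0.8 percentage points, so this is nominal within simulation error.

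**The case against.** The strongest reply is that the SAP never says these answers are dropped. A reader might infer that the plan itself commits to comparing non-randomized groups, or that the test has a known, inflated false-positive rate. The documents support neither. The handling is unspecified, and the inflation comes entirely from an assumed difference in how prior-glargine users answer. When that difference is zero, dropping the answers does no harm. The direction is also unknown, so the bias could favor either arm.

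A reader might also infer that the option can only ever appear in the glargine arm. That is true of the design, but participants choose the response themselves, so stray use is possible in either arm. The documents also do not say whether a U-300 user moved to the 100 units/mL study product has kept the same insulin.

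Finally, the endpoint is defined as a frequency of responses, is tertiary, and lies outside the multiplicity scheme. A frequency table could already show the not-applicable count.

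All of this stands, and it limits the size and importance of the point. It does not remove it. A between-arm test is specified, an answer off its scale will occur by design in one arm, and neither obvious handling gives a sound comparison.

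**Conclusion.** The point holds as a gap in a specified analysis. SAP 4.5.3.1 applies a rank test without a rule for an option that, by design, belongs to one arm. The default of dropping it selects on pre-study insulin in that arm only, and ranking it imposes an order that does not exist.

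That structure follows from the eligibility criteria and the item wording and needs no assumption about data. The size does. With 284 per arm and an assumed 20% to 60% share on glargine before the study, rejection under no effect is about 5% with no difference in answers, 8% to 23% at 0.25 SD, and 17% to 70% at 0.5 SD. These are illustrations and do not estimate the trial's error rate. The priority is low, since no primary or key secondary conclusion depends on this item.

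**What to change.** Add a short rule to SAP 4.5.3.1:
- Report not-applicable answers as a count by arm and never rank them.
- Run the rank sum test, in both arms, only among participants whose recorded pre-study basal insulin was not U-100 glargine. This group is fixed before randomization, so the comparison remains randomized.
- State how U-300 users are classified, by recorded insulin and identically in both arms, and how a not-applicable answer from someone inside the tested group is treated.

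Alternatively, report frequencies by arm without a p-value.

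No new data are needed, because SAP 6.1 already summarizes the type of pre-study basal insulin. The grouping in SAP 4.7.2.1 is too coarse for this purpose, since it separates typical once-daily insulins from U-300 and twice-daily NPH and does not isolate U-100 glargine. If the SAP is closed, SAP 4.1 allows a change of method to be described and justified in the clinical study report.

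The cost is a smaller LY3209590 group in the test, about 227, 170 or 114 instead of 284 at assumed shares of 20%, 40% or 60%, and a result that applies to participants who changed basal insulin.

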##### 4.5.3.2. EQ-5D-5L

The EQ-5D-5L (EuroQol 2019) is a standardized 5-item self-administered instrument for use as a measure of health outcome. It provides a simple descriptive profile and a single index value for health status that can be used in the clinical and economic evaluation of health care as well as population health surveys. The EQ-5D-5L assesses 5 dimensions of health:

- mobility
- selfcare
- usual activities
- pain/discomfort
- anxiety/depression

The 5L version, scores each dimension at 5 levels:

- no problems
- slight problems
- moderate problems
- severe problems
- unable to perform/extreme problems

In addition to the health profile, a single health state index value can be derived based on a formula that attaches weights to each of the levels in each dimension. This index value ranges between less than 0 (where 0 is a health state equivalent to death; negative values are valued as worse than dead) to 1 (perfect health).

The second part of the questionnaire consists of EQ Visual Analog Scale (VAS) which records the respondent's self-rated health status. The participant rates his or her perceived health from 0 (the worst imaginable health) to 100 (the best imaginable health). In conjunction with the health state data, it provides a composite picture of the respondent's health status.

The frequency and proportion of each level for a given item will be summarized by study treatment for the scheduled visit. The last non-missing postbaseline observations up to Week 26 (Visit 23) on EQ-5D-5L index, EQ VAS score and their change from baseline will be analyzed by an ANCOVA model using the independent variables of treatment, strata (country, baseline HbA1c stratum ( $<8.0\%$ ,  $\geq 8.0\%$ ), and routine use of personal CGM or FGM at randomization), and baseline value of the dependent variable.

## 4.6. Safety Analyses

Safety measures include treatment exposure, adverse event (AE), vital signs, weight, hypoglycemia, laboratory measures and immunogenicity. All safety analyses will be based on the SS. Unless otherwise specified, safety analysis period will include both treatment period and follow-up period as specified in Section 4.1. Percentages will be calculated using the safety population as the denominator. For events that are gender-specific, the denominator and computation of the percentage will include only participants from the given sex. Unless otherwise noted, Fisher's exact test will be used for treatment comparison, risk difference and 95% confidence intervals will be provided.

For continuous safety variables (for example, laboratory measures, vital signs, and weight), descriptive statistics for the observed values and change from baseline at scheduled visits during the treatment period and follow-up period will be provided. For some selected laboratory measures (i.e. liver enzyme tests, lipid measures), observed values, change from baseline and percentage change from baseline will be analyzed for the log-transformed values by the MMRM model using treatment, visit, and treatment by visit as fixed effects, baseline of the dependent variable as a covariate, and compound symmetry as the variance-covariance structure.

The incidence and event rate of participant-reported and CGM-based hypoglycemia will be summarized by treatment and analysis period for different types of hypoglycemia. Analysis details are provided in Section 0.

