**Figure BDCV 2.1. Illustration of graphical multiple testing procedure with initial  $\alpha$  allocation and weights.**

### 3. Analysis Sets

This table defines the populations and data sets for the purpose of analysis.

Analysis Populations/ Data Sets	Description
Entered Population	All participants who sign the informed consent form
Randomized Population	All randomized participants. Participants will be analyzed according to the treatment they were assigned.
Modified Intent-to-Treat (mITT) Population	All randomized participants who took at least 1 dose of study treatment. Participants will be analyzed according to the treatment they were assigned.
Efficacy Analysis Set 1 (EAS1) for treatment regimen estimand on efficacy measures	
The data will include
 
 
• mITT Population, excluding participants discontinuing the study treatment due to inadvertent enrollment, and
 
• all measurements regardless of the use of study treatment or the initiation of rescue therapy.
 

Efficacy Analysis Set 2 (EAS2) for efficacy estimand and for other secondary/tertiary objectives on efficacy measures	
The data will include
 
 
• mITT Population, excluding participants discontinuing the study treatment due to inadvertent enrollment, and
 
• measurements up to the early discontinuation of study treatment or the initiation of rescue therapy.
 
 
The data cutoff for participants who had intercurrent events is defined by the earliest date from below dates for individual participants other than the analysis for study dose:
 
 
• the date of last study dose + 10 days for LY3209590, or +1 day for glargine
 
• the start date of the first treatment of rescue therapy
 
 
The data cutoff for the analysis on study dose is defined by the earliest date from below dates for individual participants:
 
 
• the date of last study dose
 
• the start date of the first treatment of rescue therapy
 

Safety Analysis Set (SS)	
The data will include
 
 
• mITT Population, and
 
• all measurements regardless of the use of study treatment or the initiation of rescue therapy.
 

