Incidence of Level 2 hypoglycemic events: 
 
• All documented
 
	Baseline, 0-6, 0-12, 0-26, 12-26 weeks, post-treatment period	Logistic regression with treatment, baseline HbA1c and baseline Level 2 hypoglycemia incidence as covariates.
Incidence of Level 3 hypoglycemic events: 
 
• All documented
 
	Baseline, 0-26 weeks, post-treatment period	Logistic regression with treatment and baseline HbA1c as covariates.

Endpoint	Analysis Period	Statistical Method
Incidence of Level 2/3 hypoglycemic events: 
 
• All documented
 
• Nocturnal
 
• Non-nocturnal
 
	Baseline, 0-6, 0-12, 0-26, 12-26 weeks, post-treatment period	Logistic regression with treatment, baseline HbA1c and baseline hypoglycemia incidence of the same hypoglycemia type as covariates.
Potential Persistent-recurrent hypoglycemic events 
 
• Identified by investigator
 
• Identified by prespecified criteria (defined in Section 6.11)
 
	Safety analysis period (see definition in Section 4.6)	The number of participants with at least 1 event will be summarized and compared by Fisher's exact test. The number of events will also be provided. Listings of the events will also be provided.

Abbreviations: HbA1c = hemoglobin A1c; Level 2/3= Level 2 and Level 3 composite.

Note: The yearly hypoglycemia rate during defined period is calculated by number of hypoglycemic events within the period/number of days patient at risk within the period \*365.25. For rare events, 100 year rate will be provided. The hypoglycemia incidence during defined period indicates if the patient has at least 1 hypoglycemia event within the period (Yes/No).

Note: Group comparisons for hypoglycemia incidence and rate at baseline , baseline HbA1c is not included in the model.

Note: The hypoglycemia rate during the defined period is calculated by the number of hypoglycemia events within the period/number of days a participant is at risk within the period. The hypoglycemia incidence during the defined period indicates if the participant has at least 1 hypoglycemia event within the period (yes/no).

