#### 4.6.2.2.2. Hypoglycemic Events derived from CGM

Level 2, Level 2 ending with BG value  $\geq 70$  mg/dL, and Level 1 or Level 2 hypoglycemic events collected from the sponsor provided CGM are defined in Appendix 6, Section 6.6.2. The analysis for incidence, event rate, and duration are described in the table below. All data are included in the analysis. Missing data will be handled as described in Appendix 6.

Endpoint	CGM Session*	Statistical Method
Event rate of Level 1 or Level 2 hypoglycemic events (events/participant/year): 
 
• 24-hour
 
	Baseline, 0-4, 8-12, 22-26, 0-26 weeks, post-treatment period	Negative binomial regression with treatment, baseline HbA1c and baseline Level 1 or Level 2 hypoglycemia rate as covariates, log (exposure/365.25 days) as the offset in the model.
Event rate of Level 2 hypoglycemic events (events/participant/year): 
 
• 24-hour
 
	Baseline, 0-4, 8-12, 22-26, 0-26 weeks, post-treatment period	Negative binomial regression with treatment, baseline HbA1c and baseline Level 2 hypoglycemia rate as covariates, log (exposure/365.25 days) as the offset in the model.

Endpoint	CGM Session*	Statistical Method
Event rate of Level 2 hypoglycemic events ending with $\geq 70$ mg/dL (events/participant/year): • 24-hour	Baseline, 0-4, 8-12, 22-26, 0-26 weeks, post-treatment period	Negative binomial regression with treatment, baseline HbA1c and baseline rate for Level 2 hypoglycemia ending with $\geq 70$ mg/dL as covariates, log (exposure/365.25 days) as the offset in the model.
Incidence of Level 1 or Level 2 hypoglycemic events: • 24-hour	Baseline, 0-4, 8-12, 22-26, 0-26 weeks, post-treatment period	Logistic regression with treatment, baseline HbA1c and baseline Level 1 or Level 2 hypoglycemia rate as covariates.  The total number of episodes, number of episodes that includes Level 2 hypoglycemia episodes, and number of episodes that include glucose readings $<54$ mg/dL(3.0 mmol/L) but no Level 2 hypoglycemia episodes will be summarized for each CGM session.
Incidence of Level 2 hypoglycemic events: • 24-hour	Baseline, 0-4, 8-12, 22-26, 0-26 weeks, post-treatment period	Logistic regression with treatment, baseline HbA1c and baseline Level 2 hypoglycemia incidence as covariates.

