#### 4.6.2.3. Laboratory and Adverse Event for Hepatic Safety

Hepatic labs include

- alanine aminotransferase (ALT)
- aspartate aminotransferase (AST)
- total bilirubin (TBL)
- direct bilirubin (DBL)

- serum alkaline phosphatase (ALP), and
- gamma-glutamyltransferase (GGT).

When criteria are met for hepatic evaluations, investigators will conduct close monitoring of hepatic symptoms and liver tests, perform a comprehensive evaluation for alternative causes of abnormal liver tests, and complete follow-up hepatic safety CRFs.

The table below lists summary TFLs for the analysis of hepatic laboratory data.

Analysis	Details
Abnormal postbaseline categories – hepatic safety parameters	
ALT: The number and percentage of participants with a measurement greater than or equal to 1 time (1X), 3 times (3X), 5 times (5X), 10 times (10X), and 20 times (20X) the performing laboratory ULN during the postbaseline period will be summarized for all participants with a postbaseline value.
 
AST: The number and percentage of participants with a measurement greater than or equal to 1 time (1X), 3 times (3X), 5 times (5X), 10 times (10X), and 20 times (20X) the performing laboratory ULN during the postbaseline period will be summarized for all participants with a postbaseline value.
 
ALP: The number and percentage of participants with a measurement greater than or equal to 2 times (2X) and 3 times (3X) the performing laboratory ULN during the postbaseline period will be summarized for all participants with a postbaseline value.
 
TBL: The number and percentage of participants with a measurement greater than or equal to 2 times (2X), 5 times (5X), and 8 times (8X) the performing laboratory ULN during the postbaseline period will be summarized for all participants with a postbaseline value.
 
DBL: The number and percentage of participants with a measurement greater than or equal to 2 times (2X) and 5 times (5X) the performing laboratory ULN during the postbaseline period will be summarized for all participants with a postbaseline value.
 
GGT: The number and percentage of participants with a measurement greater than or equal to 2 times (2X) the performing laboratory ULN during the postbaseline period will be summarized for all participants with a postbaseline value.

Analysis	Details

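### Participant-reported hypoglycemia incidence in Weeks 12-26 and post-treatment counts people with no time at risk as event-free; for CGM sessions the denominator is not stated

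*SAP*

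**What the plan says.** SAP 4.6 gives the default for safety outputs: "Percentages will be calculated using the safety population as the denominator". SAP 4.1 repeats it. SAP 4.6 also places hypoglycemia under this heading: "The incidence and event rate of participant-reported and CGM-based hypoglycemia will be summarized by treatment and analysis period". The Safety Analysis Set (SAP 3) is everyone who took at least one dose, with "all measurements regardless of the use of study treatment or the initiation of rescue therapy".

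For participant-reported events, SAP 4.6.2.2.1 lists these windows for Level 1, Level 2 and Level 2/3 incidence: "Baseline, 0-6, 0-12, 0-26, 12-26 weeks, post-treatment period". A table note defines the outcome: "The hypoglycemia incidence during the defined period indicates if the participant has at least 1 hypoglycemia event within the period (yes/no". The model is a logistic regression without an exposure term. The matching rate is events divided by days at risk in the window, modelled by negative binomial regression with log exposure as offset.

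The table in SAP 4.1 ends the treatment period of an early stopper at last dose plus 10 days for LY3209590 or plus 1 day for glargine. The post-treatment period starts the day after that and runs to the last date in the study.

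For CGM events, SAP 4.6.2.2.2 says: "All data are included in the analysis. Missing data will be handled as described in Appendix 6". Appendix 6 bases CGM derivations on valid days and sessions unless otherwise specified, asks for 3 valid days per session, and treats gaps longer than 15 minutes as missing.

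Elsewhere the SAP does narrow the default. Hepatic laboratory categories "will be summarized for all participants with a postbaseline value", and the blood pressure categories in SAP 4.6.2.5 need at least one postbaseline measurement.

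**The concern.** A participant whose treatment period closed before Week 12 cannot have a treatment-period event in Weeks 12-26. On the text as written, that person stays in the denominator and the flag reads no. Absence of observation becomes absence of hypoglycemia.

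The rate for the same endpoint and window cannot treat the person that way: events divided by zero days, and the log of zero exposure, are both undefined. Incidence and rate in adjacent rows would then describe different participants, and the SAP does not say so.

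Weeks 12-26 follow the weekly titration period (Protocol 6.5), so this window shows hypoglycemia once doses are meant to have settled. Counting the unobserved as event-free lowers incidence in both arms. If early stopping differs between arms, it also tilts the comparison toward the arm that loses more people, in an open-label trial.

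**Working it through.** **Inputs**
- 670 randomized 1:1, so 335 per arm, with 15% dropout at Week 26 (SAP 5).
- Treatment period of an early stopper: last dose +10 days (LY3209590) or +1 day (glargine) (SAP 4.1).
- Week 12 = day 84; Week 26 = day 182.
- Assumptions: the 15% is early treatment discontinuation, with last-dose dates spread uniformly over the 182 days. The documents give neither the timing nor an expected incidence percentage.

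**The plan's own figure.** 335 × (1 − 0.15) = 284.75, which agrees with the stated 284 completers per arm.

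**Share with no time at risk in Weeks 12-26.** The treatment period must close before day 84, so the last dose must fall before day 84 − e, where e is the extension:

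d = 0.15 × (84 − e) / 182

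- No extension: 0.15 × 84/182 = 6.9%
- Glargine, e = 1: 0.15 × 83/182 = 6.8% (about 23 of 335)
- LY3209590, e = 10: 0.15 × 74/182 = 6.1% (about 20 of 335)

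**Effect on incidence.** Reported incidence = at-risk incidence × (1 − d), so the relative understatement is d.

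| At-risk incidence (assumed) | Reported, LY3209590 | Reported, glargine |
|---|---|---|
| 10% | 9.4% | 9.3% |
| 20% | 18.8% | 18.6% |
| 30% | 28.2% | 27.9% |
| 50% | 47.0% | 46.6% |

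The SAP's planning rate for glargine gives a sense of scale: 1.1 nocturnal Level 2/3 events per year, SD 2.6. Reading the SD as annual (an assumption), the negative binomial dispersion is (2.6² − 1.1)/1.1² = 4.68. Over 14 weeks the expected count is 1.1 × 98/365.25 = 0.295, and the probability of at least one event is 1 − (1 + 4.68 × 0.295)^(−1/4.68) = 16.9%. Reported: 16.9% × (1 − 0.068) = 15.8%.

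**Effect on the comparison.** With equal d, the risk ratio is unchanged and the risk difference shrinks by the factor (1 − d). For unequal stopping, assume 18% (LY3209590) vs 12% (glargine) and an equal true incidence of 50%:
- Without the extensions: d = 0.18 × 12/26 = 8.3% and 0.12 × 12/26 = 5.5%. Reported 45.8% vs 47.2%. Odds ratio (0.458/0.542)/(0.472/0.528) = 0.95. Log odds ratio −0.056, standard error 0.155 at 335 per arm, so about 0.36 standard errors.
- With the extensions: d = 7.3% and 5.5%, reported 46.3% vs 47.3%, odds ratio 0.96.

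**Post-treatment window.** The same logic applies only to participants with no follow-up after the treatment period. Early stoppers who stay in the study have post-treatment time under SAP 4.1. The documents give no figure for those with none, so no size is calculated.

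**Outputs not affected**
- Week 0-26 e-diary incidence: every dosed participant starts at risk. Follow-up length still varies.
- Key secondary nocturnal event rate: it carries an exposure offset.
- Key secondary composite: participants who discontinue the treatment period early are scored as non-responders (SAP 4.4.1.2).

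**The case against.** **The effect is small and the outputs are supportive.** This stands. No multiplicity-controlled test moves, exposure-adjusted rates are planned for the same windows, and Level 2/3 events also get mean cumulative function plots. Table specifications sit in separate documents (SAP 1) and may already show an N per window. The SAP rule still gives a wrong percentage if followed as written.

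**People who stop treatment stay in the study, and the safety set keeps their data.** This is true (Protocol 7.1, SAP 3), and it is why the post-treatment point is limited to those with no follow-up. It does not help in Weeks 12-26, because SAP 4.1 closes the treatment period shortly after the last dose. If the team means to count off-treatment events in that window, the SAP should say so; the affected share would then fall to those who left the study.

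**Restricting to those still at risk conditions on a post-randomization outcome.** This also stands. If hypoglycemia-prone participants leave early, the restricted figure can be low too, and it is no longer a comparison of the groups as randomized. That is a reason to show both Ns. It does not justify scoring unobserved people as event-free.

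**A stronger reading: participants without CGM data in a session are also scored event-free.** A reader might infer this from the default denominator, with a larger loss at Weeks 22-26. The documents do not support it. SAP 4.6.2.2.2 refers missing data to Appendix 6, whose valid-session and gap rules point toward treating an absent session as missing, and nothing scores it as a no. What remains open is whether the statement that all data are included sets aside the valid-session rule, and which N the percentage uses.

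**Conclusion.** The point holds for participant-reported incidence in Weeks 12-26, and in the post-treatment window for participants with no follow-up there. Under 15% early stopping spread uniformly, Weeks 12-26 incidence is understated by about 6.1% (LY3209590) to 6.8% (glargine) in relative terms. The full 15% would be too high a figure, because anyone who stops inside the window keeps some time at risk. An assumed 18% vs 12% imbalance would produce a spurious odds ratio of about 0.95, well within sampling error; the documents predict no such imbalance.

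For CGM incidence the finding is only that the denominator is unclear. The primary analysis, the key secondary tests and Week 0-26 e-diary incidence do not change. The correction should be made because it is cheap and brings incidence and rate onto the same participants.

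**What to change.** In SAP 4.6.2.2.1, state that for each window the incidence percentage and the logistic model include only participants with at least 1 day at risk in that window, the same set as for the rate. Show that N by arm, with the full safety-population N alongside.

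In SAP 4.6.2.2.2, state that participants without CGM data in a session are excluded from that session's incidence, and say whether the valid-session rule of Appendix 6 applies to CGM events.

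The cost is a few sentences in the SAP and a filter in the tables. Late windows will hold slightly fewer participants, and their comparison becomes conditional on remaining at risk; a table footnote should say so.
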